## Protocol Summary

Title	XENON AND COOLING THERAPY IN BABIES AT HIGH RISK OF BRAIN INJURY FOLLOWING POOR CONDITION AT BIRTH: RANDOMISED PILOT STUDY (COOLXENON2 STUDY)
Investigators	[name] (Chief Investigator) e-mail: [contact] Mob: [name] [name] (Co-Investigator) e-mail: [contact] Mob: [name] [name] (Co-Investigator) e-mail: [contact] Mob: [name] [name] (Co-Investigator) [name] (Co-Investigator) [name] (Co-Investigator) [name] (Co-Investigator) [name] (Co-Investigator) [name] (Co-Investigator) [name] (Co-investigator)
Study Centre	St Michael's Hospital [name]
Test Article	Xenon Neonatal Breathing Device
Objectives	
Primary Objective: This is a randomised two group pilot study comparing:
 
 
i) xenon inhalation for 18 hours in combination with whole body cooling to 33.5 °C for 3 days, to
 
ii) the established treatment of cooling the body down to 33.5 °C for 3 days.
 
 
This will be applied in term newborn babies who are at moderate or high risk of brain injury following poor condition around the time of birth.
 
Our hypothesis is that during the first 2 weeks after birth using a combination of validated (in our own and others cohorts) early predictors of outcome we may observe an enhanced neuroprotective effect of the xenon-cooling combination over cooling alone and this will allow us to perform power calculations for a larger definitive neurological outcomes study of otherwise similar design.
 
Outcome predictors are based on a combination of:
 
 
1) Time in hours after birth when background activity as recorded by amplitude integrated EEG (aEEG: from single channel EEG) [1] and
 

Reference:	CH
Issue:	2
Revision:	3
Issue Date:	1 May 2013
Page	4 of 49

onset of sleep wave cycling (SWC). Time to Normal trace and SWC are both very good (PPV>90%) outcome predictors  
 2) MRI before 2 weeks of age (T1W and T2W) has a PPV of 84% in cooled infants in the TOBY trial in which we were a major recruiting centre [2] Resistance Index (RI) was not a definite predictor for cooled infants [3]). We will do the examination but not use it in the prediction. Peak value of Lactate Dehydrogenase within the first 72h of life [4, and [name] M 2012 submitted ].

**Secondary Objectives:**

We will monitor a number of variables before/during and after the period of xenon delivery. This group of physiological and biochemical parameters includes those recorded during our recently completed xenon+cooling feasibility/safety study in neonates and a few more are added .

They are:

Gas exchange: Transcutaneous oxygen saturation, end-tidal carbon dioxide concentration, blood gas data (from arterial sample), mechanical ventilation requirements (rate, peak inspiratory pressure, PEEP settings).

Haemodynamic: Systolic, mean and diastolic arterial pressure, heart rate.

Any problems during weaning and extubation, such as post-extubation stridor, use of steroids.

We have also looked at other variables in the infants cooled in our hospital (inborn or outborn) ca 30/year since 1/12/06. We chose the best matched controls (3:1) from this cooling database and compared them with the 14 infants in the recent Xenon + cooling human feasibility study (the precursor to this study),

We will also record:

- 1] Coagulopathy [INR >2, APTT> 50]
- 2] Inotrope requirement, cardiac Troponin T
- 3] Hepatic impairment, [raised Alanine aminotransferase > 40, Alkaline phosphatase > 100, peak Lactate dehydrogenase within 72h of age
- 4] Renal impairment, oliguria [urine output < 1 ml/kg/h after day 1 of life and raised creatinine > 100]
- 5] Infection [culture proven, need for antibiotics  $\geq$  5 days, raised CRP  $\sim$  within the first 24h and at 4 days of life of life]
- 6] Number of anticonvulsive drugs needed to treat seizures
- 7] Length of hospital stay
- 8] Time to full oral feed by bottle or breast
- 9] MRI assessment by T1 and T2 weighted images using the scoring system by Rutherford et al [2].
- 10] In some infants when the 3Tesla MRI scanner is available assessment of brain metabolites using magnetic resonance spectroscopy (MRS) where the ratio Lactate/N-acetyl aspartate has

Reference:	CH
Issue:	2
Revision:	3
Issue Date:	1 May 2013
Page	5 of 49

	been shown to be a good early biomarker for outcome [5].  Safety
Patient Population	Newborn infants $\geq$ 36 weeks gestation which satisfy all St Michael's Hospital standard inclusion criteria for cooling (i.e. at risk of brain injury following poor condition at birth) and which additionally satisfy the inclusion criteria of this investigation for the administration of xenon by inhalation. Cooling should be started within 3h of age and xenon within 5. Use of a shorter treatment delay in these entry criteria will optimize the possibility of finding an effect if there is one.
Population Size	16 babies in each of 2 groups
Structure	Single centre prospective randomised clinical pilot study
Duration of Participation	Xenon administration period of 18 hours. Recruitment period up to 18 months from start of study. Short and long term monitoring until 18 months of age. Therefore total study duration 3 years.
Method of Assignment	Comparative study. Neonates meeting all entry criteria can be included.
Randomisation	Patients will be randomised between cooling (standard treatment) and xenon+cooling groups as this is a comparative study. Patients will be randomised on a 1:1 basis to receive either conventional cooling therapy or cooling plus xenon therapy.
Statistical Analysis	
This is a randomised pilot study. Data presentation will include descriptive statistics only. These will be compared in the 2 treatment groups but also to recordings of the same variables in a similar group of 45 infants (recruited to cooling only from the same entry criteria) recently treated in our department (historical control data). Differences between the groups will be estimated.
 
Sample size is 16 infants in each group. In accordance with the paper by Julious (Appendix 11), 12 is a large enough number to estimate the mean value of short term outcome variables for the group. The study does of course not have the power to test outcome. The main purpose of this randomised pilot study is to examine whether early recruitment is feasible, secondly whether the short term biological markers show the expected range of values in the cooled only group as compared to our historical controls. Our advisory statistician for this study is [name] who also advised all our experimental xenon work as well as the recent clinical feasibility study.
 
By April 2013 we have recruited 8 babies to standard cooling therapy and 7 babies to xenon plus cooling; we have failed to recruit approximately the same number due to failure to commence xenon delivery at St Michael's Hospital within 5 hours of birth. This is due to the time it takes to retrieve infants from the regional hospitals. Since April 2013, our xenon delivery system has been transportable and we have so far successfully started xenon treatment on two babies in the

Reference:	CH
Issue:	2
Revision:	3
Issue Date:	1 May 2013
Page	6 of 49

	local hospital and transferred them to St Michael's Hospital while xenon was being delivered en route. This ability to commence xenon at the referring trust enabled us to recruit consecutive infants that would otherwise have been missed. We wish to assess the feasibility of recruiting now we have xenon in the ambulance by increasing the number of babies by 8.
Adverse Events	Volunteered and Elicited

Reference:	CH
Issue:	2
Revision:	3
Issue Date:	1 May 2013
Page	7 of 49

SECTION	CONTENTS	PAGE
	Confidentiality Statement	2
	Protocol Summary	3
	Overview	9
1.0	Background and Introduction	9
1.1	Background	9
1.2	Review of Literature	9
1.3	Rationale for the Study	10
2.0	Objectives	11
2.1	Primary Endpoint	11
2.2	Secondary Endpoint	12
3.0	Study Design	13

## Overview

The proposed study is planned to be a single centre study at St. Michael's Hospital Bristol, prospective randomised pilot clinical study. It may include Southmead Hospital Bristol at a later stage if recruitment is low. We have included a shorter delay for recruitment to optimize the effectiveness of hypothermia and potentially xenon. We will accept cooled infants that are <3h old and start xenon within 5h of age. In an experimental study we did not find any improvement of adding xenon if both were started at 5 hours after the insult [6], however 2h delayed xenon when HT was started immediately was more effective than HT alone [7].

The study examines the effect of inhaled xenon gas used in the treatment of newborn infants with hypoxic-ischemic encephalopathy (HIE), in combination with cooling which is the standard treatment for this condition. The hypothesis is that the xenon+cooling combination will produce better neuroprotection than the standard treatment, cooling, alone. Xenon, a rare anaesthetic gas, is almost side-effect free and shows great promise as a method of enhancing the neuroprotection offered by cooling. It is, however, extremely expensive at £25-50/L.

We propose to study 32 full term infants with moderate or severe HIE who, on clinical grounds, require mechanical ventilation and hypothermia for 72 hours. The hypothermia (cooling) will be routinely applied if the standard existing criteria for this are met except recruitment needs to be earlier, <3h rather than 6h as noted above. Candidates for the study will be randomly assigned to one of two groups: (i) the standard treatment for this condition, 72 hours of cooling, *i.e. the treatment they are already receiving*, or (ii) addition of 50% xenon concentration in the breathing gas from the mechanical ventilator for 18 hours in combination with the existing cooling regime, the cooling then continuing to 72 hours. All efforts will be made to commence delivery of the xenon and cooling as soon as possible after birth, with maximum delay of 5 hours for xenon and 3 hours for cooling. Xenon will be given in the breathing gas mixture via a special delivery system situated between the ventilator and airway of the infant. This device has been specifically developed to eliminate xenon wastage [8], without which this putative therapy would be completely unfeasible on cost grounds. It has recently been successfully used in 14 babies with the same entry criteria in our recent MHRA approved human feasibility/safety study [9]. Meetings of an independent Data Review Group will take place after the recruitment of every 4th baby during enrolment of infants to the xenon+cooling group.

## 1.0 Background and Introduction

### 1.1 Background

HIE is a major cause of severe cognitive and motor disability in term infants. Until 2005, there was no effective treatment for HIE. Since 1993 we have developed moderate hypothermia (HT) as a neuroprotective treatment culminating in a successful clinical feasibility study in Bristol 1998-9 (10 infants). This experimental work led to the "CoolCap" trial [10] followed by the UK "TOBY" trial.[11] In both trials Bristol was a major recruiting centre (PI:MT). The trials have shown that HT significantly reduced disability and cooling has now become standard treatment. Because the protection from clinically delayed HT (by 4.5h) is only partial, (absolute risk reduction 15% [12], enhancing its effectiveness as well as starting earlier is paramount. More recent clinical trials have also shown effectiveness of HT [13]. Since 2003 we have demonstrated that immediate xenon and immediate hypothermia in combination, increase cerebral protection from 35% (HT alone) to 70% in newborn rats and pigs.[14, 15] In 2011 we completed a human neonatal feasibility/safety study of 14 patients undergoing standard cooling therapy for moderate or severe perinatal asphyxia using a xenon delivery system of the same design. We experienced no technical problems due to the breathing system or use of the xenon gas (Appendix 4) nor any adverse effects related to these.

### 1.2 Review of Literature

Critical lack of oxygen delivery to the foetus during labour and delivery results in HIE in 1-3 per 1000 births at term. 60-70% of infants with moderate/severe HIE die or survive with serious disability such as cerebral palsy and/or learning difficulties. Some of the survivors are unable to walk, sit up, control head movement, feed or communicate. Until 2005 there was no treatment that had been shown to improve outcome in such infants. Since 1993 [name]'s

Reference:	CH
Issue:	2
Revision:	3
Issue Date:	1 May 2013
Page	11 of 49

group have taken moderate hypothermia (HT) as a neuroprotective treatment through all the steps of therapeutic development starting with small (rat)[16,17] and large (pig),[18,19] animal models to a clinical feasibility study in Bristol (body or head cooling in 10 infants)[18]. In collaboration with others our experimental work and clinical pilot led to the American funded “CoolCap” trial where Bristol was a major recruiting centre. The results were published in 2005 and showed a therapeutic benefit from hypothermia.[1] This study was followed by the American National Institute of Child Health and Development body cooling trial which also showed reduced mortality and improved neurological outcome in the cooled group.[22] We and colleagues in the UK (PI Denis Azzopardi) received MRC funding to carry out the largest of all the cooling trials, the “TOBY” trial recruiting a total of 325 infants. St. Michael’s Hospital was a major centre in these trials and MT is one of the principal investigators and grant holders for the TOBY trial.[11] We have received further MRC funding to carry out long term follow up of this cohort which is ongoing. Other trials in Europe [23] and Australia (ICE trial) [24] have also shown significant improvement in cooled infants.

In these 5 big trials [10,11,21-23], HT reduced death or disability from 66% to 51%. The number needed to treat (NNT) to prevent death or disability is 9. Hypothermia has also been shown to be effective in adults after cardiac arrest and is being considered for other conditions where brain injury is the major problem (e.g. stroke, head trauma).

At the end of 2006, we finished recruiting to the TOBY trial and HT became standard of care in Bristol. Our local incidence of poor outcome in this group has been further reduced to 39% [25] as compared to 48% for the cooled group in “TOBY”). Compared to our own historical controls using the same entry criteria where the incidence of poor outcome was 63% without active treatment, our Bristol cooling protocol has reduced the relative risk of a poor outcome by 38%. Thus HT improves outcome but does only partly abolish death or disability. There is clearly a need to explore other therapies that can be combined with HT to further improve outcome in this devastating condition.

For the past 8 years our research group has been investigating the rare anaesthetic noble gas xenon, which is showing great promise as a neuroprotectant in HIE. Despite being considered “noble” because it is almost inert in conventional chemical reactions, xenon is not completely inert in biological systems and has been known as an anaesthetic for decades. The group has built upon the initial work in cell cultures [26,27] by conducting both small and large animal studies of xenon+cooling with positive results. In particular a suitable delivery and monitoring system capable of providing xenon to the inhaled gas mixture of a mechanically ventilated infant in the neonatal intensive care unit has been developed and evaluated in a pig model of global HIE – replicating the clinical scenario in pigs of similar weight to human neonates. This has been developed by [name], Reader in Anaesthetics, a member of the [name] collaborative group and honorary consultant at University Hospital Bristol.

The group have recently used this system in the first human neonatal feasibility/safety trial of xenon + cooling in this group of neonates, which was carried out in Bristol over 12 months and successfully completed 05/04/2011 (Appendix 4).

We add a recent, relevant paper [48] by Sabir et al which illustrates the safety of xenon. There was no increased apoptosis after breathing xenon for 24 hours, as compared to a 10x increase breathing isofluorane.

### 1.3 Rationale for the Study

We have undertaken a series of experiments since 2003 using xenon with different dosages, durations and delays before treatment onset in our neonatal rat brain injury model and found that xenon approximately doubles the neuroprotective effect in combination with hypothermia, compared to hypothermia alone.[14, 28, 29] Since 2006 we have investigated xenon-hypothermia (XeHT) in our newborn piglet model of global hypoxia-ischemia.[8, 31] With this model we have extensively examined the effect of XeHT, Xe alone, HT alone as compared to no treatment. We have examined the effect on the brain and all organs, in particular the heart, liver, kidney and lungs. We have also examined the biochemical changes in the blood throughout the treatment period in all the treatment groups.

In brief, we have not found any adverse effect of xenon in the piglet model – and we can document:

- Improved neuroprotection compared to HT alone [15]
- Better cardiovascular stability (reduced need for inotropic support) [31]

Reference:	CH
Issue:	2
Revision:	3
Issue Date:	1 May 2013
Page	12 of 49

- No extubation delay [15]
- No increase in oxygen requirements [15]

Our large animal trial of XE-HT in piglets recently concluded with a very positive outcome supporting the result we found in rats, i.e. adding xenon to HT doubles the neuroprotection in both animal models. Also we found in both studies that HT and Xenon had additive effects with no interaction.

A human neonatal feasibility study combining cooling (the established treatment) with xenon inhalation via mechanical ventilation was completed by this group 5/4/2011. This small scale safety study was a necessary requirement before a randomised clinical trial of cooling+xenon that would examine neurological outcomes could be conducted. The findings were similar to those listed above and have been documented and are given in more detail in Appendix 4. The design was such that the xenon duration increased from 18h and 3 patients received the maximal duration of 18h xenon which has been shown to be neuroprotective in the pig model. Increasing the duration had no adverse effect on the physiological parameters.

## 2.0 Objectives

The aim of this study is to examine using primarily short term measures and secondarily long term outcomes, the potential neuroprotective effects of the cooling+xenon combination when compared to cooling alone. We will examine the feasibility of recruiting earlier than previous trials, <3h for HT and <5h for starting xenon and assess what proportion of the eligible infants we can recruit. We will compare the short term biomarkers (aEEG recovery, MRI score, LDH and time to full feeds) in the two groups with those obtained previously in our randomised dataset (infants from CoolCap and TOBY) as well as the large group cooled since 1/12/2006 under the same protocol. In these groups of children we have both short term markers as well as Bayley outcome and have shown that our combined biomarkers has a PPV of 93%.

### Primary Objective:

This is a randomised two group pilot study comparing;

- i) Adding xenon inhalation for 18 hours in combination with the (existing) whole body cooling to 33.5 °C for 3 days.
- ii) The established treatment of cooling the body down to 33.5 °C for 3 days.

This will be applied in term newborn babies who are at moderate or high risk of brain injury following poor condition around the time of birth, the purpose being to reduce long term neurological impairment resulting from their condition.

Our hypothesis is that early predictors of outcome\* will show a trend towards an enhanced neuroprotective effect of the xenon-cooling combination over cooling alone. The early predictors will allow us to perform power calculations for a much larger neurological outcomes study of otherwise similar design.

In addition we will examine the feasibility of earlier recruitment and start of xenon and whether we obtain the same early predictor data in the hypothermia-only group as we have in our previous hypothermia database.

(\*the total clinical follow up period will be much longer than this as is already the case for cooled babies in Bristol)

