## 2.1 Primary Endpoint

This is a randomised two group pilot study comparing;

- 1) xenon inhalation for 18 hours in combination with whole body cooling to 33.5 °C for 3 days, to
- 2) the established treatment of cooling the body down to 33.5 °C for 3 days.

Reference:	CH
Issue:	2
Revision:	3
Issue Date:	1 May 2013
Page	13 of 49

This will be applied in term newborn babies who display signs indicating moderate or severe brain injury following poor condition at birth.

Our hypothesis is that we may observe an enhanced neuroprotective effect of the xenon-cooling combination over cooling alone assessed initially by early outcome predictors. This will allow us to perform power calculations for a much larger neurological outcomes study of otherwise similar design. We have tested a combination of our early predictors (using our TOBY registry cooling data in 80 infants) against Bailey outcome at 18 months and found they have a positive predictive value of 94% in cooled infants

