#### **Group size calculation**

Sixteen babies will be recruited into each group (cooling+xenon vs cooling alone) at random. The cooling will be applied as standard treatment if cooling criteria are met. Addition of xenon in combination with this underlying cooling will take place in the group randomised to receive cooling + xenon.

For pilot studies of this type the recommendation is a sample size of 12 per group. The justifications for this sample size are based on

- i) Feasibility – allows convenient block sizes, for example our intention for a data review committee to review data sets at block intervals of 4 neonates.
- ii) Precision about the mean – little additional precision to be gained by having a larger group size than 12 [44].
- iii) Precision about the variance – little additional precision to be gained by having a larger group size than 12 [44].

Reference [44] presented in full in Appendix 10.

The first 15 neonates were recruited in a period where the xenon ambulance transfer system was not ready for use. The clinical staff employed to recruit and deliver the xenon in the ambulance needed time to gain experience using the system before using it independently away from the base hospital without the supervision of [name]. This has led to a similar number of babies which we failed to recruit (due to the time limitation) as the number recruited to

Reference:	CH
Issue:	2
Revision:	3
Issue Date:	1 May 2013
Page	25 of 49

xenon. We therefore wish to recruit a further 8 babies to assess the feasibility to recruit, more reliably, consecutive babies fulfilling the entry criteria within the confines of the protocol

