## 9.0 Data Analysis and Statistical Plan

### 9.1 Statistical Analysis

This is a randomised pilot study. Data presentation will include descriptive statistics only. These will be compared in the 2 treatment groups but also to recordings of the same variables in a similar group of 45 infants (recruited to cooling only from the same entry criteria) recently treated in our department (historical control data). Differences between the groups will be estimated

Sample size is 16 infants in each group. In accordance with the paper by Julius (Appendix 11), 12 is a large enough number to estimate the mean value of short term outcome variables for the group. The study does of course not have the power to test outcome. The main purpose of this randomised pilot study is to examine whether early recruitment is feasible, secondly whether the short term biological markers show the expected range of values in the cooled only group as compared to our historical controls. Our advisory statistician for this study is [name] who also advised all our experimental xenon work as well as the recent clinical feasibility study.

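### The protocol ties the size of the larger trial to the xenon effect seen on early markers, which 16 infants per arm cannot estimate well enough

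*Protocol*

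**What the plan says.** The sizing purpose appears in four places in the protocol.

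- **Protocol Summary, Primary Objective:** the key words are "we may observe an enhanced neuroprotective effect of the xenon-cooling combination over cooling alone and this will allow us to perform power calculations". The calculation meant is the one for the definitive trial to follow.
- **Section 2.0, Primary Objective:** "The early predictors will allow us to perform power calculations". This sentence does not name the observed effect, but it directly follows the hypothesis of a trend in favour of xenon.
- **Section 2.1:** the hypothesis is put again as a possible gain for xenon with cooling, judged at first on the early markers. The consequence is then drawn from it: "This will allow us to perform power calculations for a much larger neurological outcomes study of otherwise similar design".
- **Section 3.3, reason 3:** the pilot data are to go into the power calculations that set the group sizes of the larger randomised trial.

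On the pilot's own size, section 9.1 says "Sample size is 16 infants in each group", and the Summary says "Patients will be randomised on a 1:1 basis". Under Group size calculation in section 3.3, 12 per group is justified by convenient blocks, by precision of the mean ("Precision about the mean – little additional precision to be gained by having a larger group size than 12") and, in parallel words, by precision of the variance. The further 8 babies are added to assess recruitment with xenon in the ambulance. Section 9.1 plans descriptive statistics only and adds: "The study does of course not have the power to test outcome".

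Sections 3.2 and 7.5.4 also name the relationship between markers and long-term outcome as an input to sizing. The protocol does not state a minimum important difference for the larger trial.

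**The concern.** A power calculation needs a target difference, a measure of variability or an event rate, and the error rates. A small pilot can say something useful about variability and feasibility. It says very little about the difference between arms.

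The Summary and section 2.1 nevertheless make the observed difference the thing that opens the way to the calculation, while the justification of the group size covers only a mean and a variance. If the pilot difference becomes the target difference, chance largely sets the size of the next trial. A luckily large difference gives a trial that is too small. A small positive one gives a trial far larger than needed.

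**Working it through.** **The plan's own figure.** The 16 per group has no alpha, power, effect or SD behind it, so no power formula can reproduce it. It is consistent with an original plan of 12 per group plus the further 8 babies: 2 × 12 + 8 = 32 = 2 × 16.

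**Inputs.**
- From the protocol: 16 per arm and 1:1 allocation (Summary, 9.1); death or disability reduced from 66% to 51% by cooling (1.2); the claim that xenon doubles the protection from cooling (3.4); underlying mortality of about 25% (8.3).
- Assumed, because the protocol does not state them: two-sided alpha 0.05, 80% power, a normally distributed marker, and a true effect of 0.2 to 0.8 SD with 0.5 SD as the reference case.

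**Step 1: precision of the difference.** Half-width = t(2n−2) × √(2/n).
- n = 16: 2.042 × √(2/16) = 0.72 SD.
- n = 12: 2.074 × √(2/12) = 0.85 SD.

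An observed 0.5 SD therefore comes with 0.5 ± 0.72, that is −0.22 to 1.22 SD. Sizing with n = 2(1.96 + 0.842)²/d² = 15.70/d² gives:
- d = 0.5: 15.70/0.25 = 62.8, so 63 per arm.
- d = 1.22: 15.70/1.488 = 10.6, so 11 per arm.
- The lower limit lies on the side of harm and gives no usable size.

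For a binary marker the half-width is 1.96 × √(2p(1−p)/16), which is 34 points at p = 0.39 and 35 points at p = 0.51.

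**Step 2: precision of the SD.** On 30 degrees of freedom the 95% limits for the pooled SD are 0.80 to 1.34 times the estimate. The pilot can thus inform variability moderately well.

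**Step 3: what sizing on the observed effect does.** In 400,000 simulated pilots of 16 per arm, the observed effect was the difference divided by the estimated pooled SD. The next trial was sized from it by the formula above whenever it was positive, and its power was then computed at the true effect.

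At a true effect of 0.5 SD:
- The observed effect has a 95% range of about −0.20 to 1.28 SD, and 8% of pilots show no effect or the wrong sign.
- Among favourable pilots, the planned size per arm runs from about 16 to 570 (10th to 90th percentile) when 63 are needed.
- Among favourable pilots, true power averages about 70%. It is below 80% in about 54% and below 50% in about 30%.

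| True effect | Below 80% power, given a favourable pilot |
|---|---|
| 0.2 SD | about 70% |
| 0.3 SD | about 63% |
| 0.5 SD | about 54% |
| 0.8 SD | about 50% |

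If only about 12 per arm had complete markers (16 × 0.75, assuming that every death removes a data set), the figures at 0.5 SD would be about 56% and 34%.

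**Step 4: the protocol's own hope.** Reading doubled protection as a further 15 points (66 − 51 = 15; 51 − 15 = 36), the comparison of 51% with 36% needs 171 per arm. Sized on a favourable pilot, about 65% of next trials fall short of 80% power, about 47% have less than 50%, and the median planned size is 100 per arm.

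**Step 5: the alternative.** With the target fixed at 0.5 SD and only the pooled SD taken from the pilot, the size per arm runs from about 44 to 85 and power falls below 50% in about 1% of cases. Power is still slightly under 80% about half the time, because the SD is itself estimated. The gain is that severe underpowering and absurd sizes disappear.

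**The case against.** **The wording can be read more kindly.** The sentence in section 2.0 fits the use of SDs and control-arm levels only. In the Summary and section 2.1, the word that links effect and power calculation is somewhat loose, and nowhere does the protocol say that the target difference will equal the pilot difference. Sections 3.2 and 7.5.4 offer another route, through the marker-outcome relationship. This stands for section 2.0 taken alone. It does not remove the problem, because the Summary and section 2.1 place observing an enhanced effect immediately before the calculation it is said to allow, and no other source for the target difference is given.

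**A reader might infer that sizing is the pilot's main product.** The documents do not support that. The Summary and section 9.1 put feasibility of early recruitment first and agreement of the cooled-only markers with historical controls second. Section 3.3 lists sizing third of three.

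**A reader might also infer that an unfavourable pilot would end the treatment.** The protocol has no go/no-go rule on the observed effect. Its stopping rule in section 8.3 concerns mortality.

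**It would be too strong to say the next trial would usually be underpowered.** The 54% is conditional on a favourable pilot. Over all pilots in that scenario the share is 0.54 × 0.92 = about 50%, and it is also about 50% at a true effect of 0.8 SD.

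**Taking control-arm inputs from 16 infants would repeat the fault.** A 39% rate from 16 has a half-width of 1.96 × √(0.39 × 0.61/16) = 24 points, and a variance on 15 degrees of freedom has limits of 0.55 to 2.40 times the estimate. This is right, and the fix allows for it.

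**Nothing in the conduct of this trial changes.** That is true, and the larger trial will have its own protocol. The statement about power in section 9.1 is candid and does not contradict the plan. The issue is a stated purpose that the design cannot serve.

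**Conclusion.** The concern holds as a mismatch between a stated use of the pilot and what its size can support. The Summary and section 2.1 tie the larger trial's power calculation to the observed xenon effect, and section 3.3 uses the pilot data to set group sizes. The 12-per-group rule covers a mean and a variance only.

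The imprecision of 0.72 SD depends only on 16 per arm and a roughly normal marker. The consequences for the next trial rest on assumed true effects, a target of 80% power, and a larger trial that follows a favourable pilot. The spread of planned sizes, about 16 to 570 against 63 at a true 0.5 SD, shows the problem more clearly than the share below 80% does. Moving from a marker effect to an 18-month outcome would add uncertainty that is not counted here.

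The point should be corrected, but it does not affect the validity of the pilot's feasibility and descriptive aims.

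**What to change.** Amend the Summary, section 2.0, section 2.1 and section 3.3 (reason 3) to state the following.

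1. The target difference for the larger trial will be set in advance as the smallest clinically worthwhile difference in that trial's own 18-month outcome. It will not be the difference seen in the pilot.
2. The pilot supplies the proportion of eligible infants recruited, the completeness of data, and the pooled SD of the markers with confidence limits.
3. The control-arm event rate and SD will be taken from the pilot together with the larger sources the protocol already cites: the local cooled cohort (39% poor outcome), the earlier cooling trials (48% in the cooled group of one, 51% across five) and the 45 historical controls.
4. The pilot difference between arms will be reported with its confidence interval, as descriptive only.

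The cost is wording. Recruitment, treatment, data collection and the safety rules are untouched.
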